7.2.6 Pharmacokinetic assessments

PK samples will be collected in the morning after the second PSG night, after lights on, approximately 9–10 h post-dose (i.e., 30–90 min after lights on) at Visit 6 and Visit 8 or in the event of excessive sleepiness based on the investigator's opinion.

The date and the time of blood sample collection will be entered in the eCRF. The date and time of the last study treatment dosing before blood draw will be entered in the eCRF. The site personnel will ship the plasma samples to the central laboratory. The central laboratory will ship the samples to Idorsia Drug Metabolism and Pharmacokinetics department, who are in charge of the PK sample analysis.

Details about the collection, sampling, storage, and shipment procedures can be found in the laboratory manual.

8 STUDY COMPLETION AND POST-STUDY TREATMENT / MEDICAL CARE

8.1 Study completion as per protocol

A subject who completes the study treatment phase and the safety follow-up phase is considered to have completed the study as per protocol. Subjects who completed the study until the end of the run-out period will have the possibility to participate in the extension study ID-078A303 and will complete the safety follow-up phase at the end of the extension.

8.2 Premature withdrawal from study

Subjects may voluntarily withdraw from the study without justification for any reason at any time. Subjects are considered withdrawn from study if they state an intention to

withdraw further participation in all components of the study (i.e., withdrawal of consent), die, or are lost to follow-up. If a subject withdraws consent, no further data will be collected in the eCRF from the date of withdrawal onward. Withdrawal from the study may also result from a decision by Idorsia for any reason, including premature termination or suspension of the study.

Subjects are considered as lost to follow-up if all reasonable attempts by the investigator to communicate with the individual failed. The site must take preventive measures to avoid a subject being lost to follow-up (e.g., document different ways of contact such as telephone number, home address, email address, person to be contacted if the subject cannot be reached). If the subject cannot be reached, the site must make a reasonable effort to contact the subject, document all attempts, and enter the loss of follow-up information into the eCRF. The following methods must be used: at least three telephone calls must be placed to the last available telephone number and one registered letter must be sent by post to the last available home address. Additional methods may be acceptable if they are compliant with local rules/regulations (e.g., a visit by site personnel to the subject's home), respecting the subject's right to privacy. If the subject is still unreachable after all contact attempts listed above, he/she will be considered to be lost to follow-up.

If premature withdrawal occurs for any reason, the reason (if known) for premature withdrawal from the study (e.g., withdrawal by subject, AE, lost to follow-up, death) must be recorded in the eCRF.

If, for whatever reason (except death or loss-to-follow-up), a subject is withdrawn from the study, the investigator should make efforts to schedule a last appointment / telephone call to assess the safety and well-being of the subject, collect unused study treatment and discuss follow-up medical care. Data obtained during this last appointment / telephone call will be recorded in the subjects' medical records but it will not be collected in the eCRF. The investigator must provide follow-up medical care for all subjects who are prematurely withdrawn from the study, or must refer them for appropriate ongoing care, as described in Section 8.4.

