9.1.4 Reporting of adverse events

The investigator will ask the subject to report all AEs at each study visit, including the telephone calls.

All AEs with an onset date after signing of informed consent and up to EOS for subjects that are not enrolled in ID-078A303 extension study must be recorded on AE pages of the eCRF.

All AEs with an onset date after signing of informed consent, and up to enrollment in the ID-078A303 (i.e., ID-078A301 EOT) for subjects that are participating in the extension study, must be recorded on AE pages of the ID-078A301 eCRF.

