9.2.2 Reporting of serious adverse events

All SAEs occurring after signing of informed consent up to EOS must be reported on AE pages in the eCRF and on an SAE form, regardless of the investigator-attributed causal relationship with study treatment or study-mandated procedures.

All SAEs with an onset date after signing of informed consent and up to enrollment in ID-078A303 (i.e., ID-078A301 EOT) for subjects that are participating in the extension study must be recorded on AE pages of the ID-078A301 eCRF.

An SAE is defined as related to protocol-mandated procedures if it appears to have a reasonable possibility of a causal relationship to either the study design or to protocol-mandated procedures (e.g., discontinuation of a subject's previous treatment during a washout period, leading to exacerbation of underlying disease).

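### Protocol 8.2 keeps data from the last safety contact off the eCRF even where consent stands, in conflict with the AE and SAE recording rules in 9.1.4 and 9.2.2

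*Protocol*

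**What the plan says.** Protocol 8.2 contains two separate rules on data after withdrawal.

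- **Consent rule.** "If a subject withdraws consent, no further data will be collected in the eCRF from the date of withdrawal onward".
- **Last-contact rule.** "If, for whatever reason (except death or loss-to-follow-up), a subject is withdrawn from the study", the investigator should try to arrange a final appointment or call to check on safety. The data from it go to the "medical records but it will not be collected in the eCRF". No exception is made for AEs or SAEs.

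The same section allows withdrawal without any act by the subject: "Withdrawal from the study may also result from a decision by Idorsia for any reason", with study termination or suspension given as examples. Protocol 1.4.2 also lets the investigator end a subject's participation.

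The recording rules are set by time, not by contact. Protocol 9.1.4 covers "All AEs with an onset date after signing of informed consent and up to EOS" for subjects who do not enter the extension. Protocol 9.2.2 says "All SAEs occurring after signing of informed consent up to EOS must be reported on AE pages in the eCRF". Neither exempts withdrawn subjects.

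Protocol 3.1.1.3 sets EOS at the Day 115 call or at entry to the extension study. It gives special dates for consent withdrawal (the date of withdrawal) and loss to follow-up (the last successful contact). It gives none for withdrawal by the sponsor or the investigator.

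**The concern.** The consent rule already protects a subject who has refused further data collection. The last-contact rule is wider, and where the sponsor or the investigator ends participation the documents give no consent ground for it.

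The rules also work on different keys. The last-contact rule turns on when the site learns of an event; 9.1.4 turns on when the event began. A subject may have an AE on double-blind treatment, be withdrawn before the next visit, and mention the event only at the closing call. One section tells the site to enter it and another tells it not to, and the protocol does not say which prevails.

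At stake is the completeness of the AE tables in SAP 7.2. The eCRF AE pages are the only AE source that the protocol describes for them. An SAE learnt at this contact would go to drug safety on the SAE form under 9.2.5, so it could sit in the safety database and be absent from the clinical one.

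**Working it through.** No sample size, power or rate is involved, so the check sets the passages side by side. Take an AE first reported at the last contact and vary two things: whether consent was withdrawn, and how EOS is read where 3.1.1.3 is silent.

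| Case | Onset of AE | 9.1.4 / 9.2.2 | 8.2 last-contact rule | Conflict |
|---|---|---|---|---|
| Consent withdrawn; EOS = withdrawal date | Before withdrawal | Required | Barred | Yes |
| Consent withdrawn; EOS = withdrawal date | After withdrawal | Not required | Barred | No |
| Consent stands; EOS read as Day 115 | Before withdrawal | Required | Barred | Yes |
| Consent stands; EOS read as Day 115 | Between withdrawal and last contact | Required | Barred | Yes |
| Consent stands; EOS read as withdrawal date | Before withdrawal | Required | Barred | Yes |
| Consent stands; EOS read as withdrawal date | Between withdrawal and last contact | Not required | Barred | No |

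1. **Onset before withdrawal.** The sections conflict in every case, whichever way EOS is read.
2. **Onset after withdrawal.** They conflict only if consent stands and EOS is taken as Day 115. For sponsor and investigator withdrawals that is the only general definition 3.1.1.3 leaves.
3. **Where the bar has a basis.** In the two consent rows the subject's refusal may justify keeping data out. In the other four the documents offer no such ground.
4. **Effect on the tables.** SAP 13.3 says that TEAEs starting in the safety follow-up period are only listed, so some late events would not be tabulated anyway. An AE with onset in the double-blind study period (SAP 12.2) belongs in the tables, and that includes on-treatment events first mentioned at the last contact.
5. **What is not affected.** AEs entered at earlier visits stay in the eCRF.

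**The case against.** The strongest reply is that the rule hardly bites outside consent withdrawal. Protocol 5.1.9 and 8.2 count subjects as withdrawn if they withdraw consent, die or are lost to follow-up. The last-contact rule excludes death and loss to follow-up, which leaves mainly consent withdrawal. There EOS is the withdrawal date, and a later contact falls after it. The sponsor route is illustrated by termination or suspension, where Protocol 8.3 lets the sponsor issue further instructions. The reasons listed in 8.2 ("withdrawal by subject, AE, lost to follow-up, death") include an AE, but that is a field to complete. It does not show a class of AE withdrawals in which consent stands, since a subject may withdraw consent because of an AE.

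A reader might also infer that the rule drops events in the very subjects most likely to have tolerability problems. Protocol 5.1.9 does not support that. A subject who only stops treatment is not withdrawn, is followed to Day 115, and is recommended to have safety assessments within a week of the last double-blind dose. Subjects who stop treatment for tolerability but stay in the study are therefore outside the rule.

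Finally, 9.1.4 and 9.2.2 are mandatory in wording. A site that follows them would record the event, and 9.2.5 carries SAEs to drug safety regardless.

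All of this stands as a limit on size. It does not remove the conflict. The last-contact rule is written for every reason except two, it sits beside a separate consent rule that would otherwise suffice, and even under consent withdrawal an AE with earlier onset receives opposite instructions.

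**Conclusion.** The conflict between 8.2 and 9.1.4/9.2.2 is real and should be reconciled. Severity is minor. The affected AEs may be missing from the TEAE and AESI tables; whether they are depends on which section a site follows, so this is a risk of omission and not a demonstrated loss.

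The size cannot be computed. The documents give no study-withdrawal rate, no split by consent, sponsor or investigator, and no AE rate for withdrawn subjects, so any count per arm would rest on outside assumptions. The nearest figures are in SAP 6.1.4, for a 1-month Phase 2 study: 14 of 356 subjects (14/356 = 3.9%) stopped treatment early, 4 of them for AEs and 2 for withdrawal of consent (2/356 = 0.6%). These are treatment discontinuations, so they do not measure the group at issue. The SAP expects a slightly higher rate of intercurrent events in Phase 3. The view that the group is small rests on this and on 5.1.9.

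A reader might further infer that the loss differs between arms and flatters the arm with more withdrawals. That would need unequal withdrawals subject to the rule, which nothing in the documents shows. SAP 6.1.4 reports no evident difference between groups in the Phase 2 rates of, or reasons for, stopping treatment. The primary efficacy analysis is not in question here.

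**What to change.** Amend the last paragraph of Protocol 8.2, with a matching addition to 3.1.1.3:

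- Limit the no-eCRF rule to data that the subject has refused by withdrawing consent.
- For withdrawal by the sponsor or the investigator, record AEs and SAEs learnt at the last contact on the eCRF AE pages, and define EOS for these subjects in 3.1.1.3.
- For consent withdrawal, state that AEs and SAEs with onset before the withdrawal date are recorded where the subject's consent allows. Relying on an enquiry made before consent is withdrawn would not be enough, because withdrawal can come without warning.

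The last contact is already planned, so no visit or procedure is added. The cost is a short wording change, eCRF completion guidance and slightly more data entry.

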8.3 Premature termination or suspension of the study

Idorsia reserves the right to terminate the study at any time globally or locally. Investigators can terminate the participation of their site in the study at any time.

If the study is prematurely suspended or terminated, Idorsia will promptly inform the investigators, IECs/IRBs and health authorities, as appropriate, and provide the reasons for the suspension or termination.

If the study is suspended or prematurely terminated for any reason, the investigator – in agreement with Idorsia – must promptly inform all enrolled subjects and ensure their

appropriate treatment and follow-up, as described in Section 8.4. Idorsia may inform the investigator of additional procedures to be followed in order to ensure that adequate consideration is given to the protection of the subjects' interests.

In addition, if the investigator suspends or terminates the participation in the study without prior agreement from Idorsia, the investigator must promptly inform Idorsia personnel and the IEC/IRB, and provide both with a detailed written explanation of the termination or suspension.

If the IEC/IRB suspends or terminates its approval / favorable opinion of the study, the investigator must promptly notify Idorsia personnel and provide a detailed written explanation of the termination or suspension.

8.4 Medical care of subjects after study completion / withdrawal from study

After the subject's study completion or premature withdrawal from the study, whichever applies, the investigator/delegate will explain to subjects what treatment / medical care is necessary and available according to local regulations.

9 SAFETY DEFINITIONS AND REPORTING REQUIREMENTS

9.1 Adverse events

9.1.1 Definition of adverse events

An AE is any untoward medical occurrence, i.e., any unfavorable and unintended sign, including an abnormal laboratory finding, symptom, or disease that occurs in a subject during the course of the study, whether or not considered by the investigator as related to study treatment.

A TEAE is any AE temporally associated with the use of study treatment (i.e., emerging from DB study treatment initiation until up to 30 days after DB study treatment discontinuation or until enrollment into the extension study) whether or not considered by the investigator as related to study treatment.

AEs include:

- Exacerbation of a pre-existing disease.
- Increase in frequency or intensity of a pre-existing episodic disease or medical condition.
- Disease or medical condition detected or diagnosed during the course of the study even though it may have been present prior to the start of the study.
- Continuous persistent disease or symptoms present at study start that worsen following the signing of informed consent.

- Abnormal assessments, e.g., change on physical examination, ECG findings, if they represent a clinically significant finding that was not present at study start or worsened during the course of the study.
- Laboratory test abnormalities if they represent a clinically significant finding, symptomatic or not, which was not present at study start or worsened during the course of the study, or led to interruption or permanent discontinuation of study treatment.

Overdose, misuse, abuse of the study treatment and study treatment errors will be reported as an AE.

The ISB will adjudicate treatment-emergent AESIs which are similar to, or indicate:

- narcolepsy-like symptoms (i.e., EDS, cataplexy and complex sleep behavior events including hallucinations/sleep paralysis)
- suicide/self-injury

A treatment-emergent AESI is any AESI emerging from DB study treatment initiation until up to 30 days after DB study treatment discontinuation or until enrollment into the extension study.

9.1.2 Intensity of adverse events

The intensity of clinical AEs is graded on a three-point scale – mild, moderate, severe – and is reported on specific AE pages of the eCRF.

Any increases in intensity of an AE during the study will be reported in the eCRF.

The three categories of intensity are defined as follows:

□ Mild

The event may be noticeable to the subject. It does not usually influence daily activities, and normally does not require intervention.

□ Moderate

The event may make the subject uncomfortable. Performance of daily activities may be influenced, and intervention may be needed.

□ Severe

The event may cause noticeable discomfort and usually interferes with daily activities. The subject may not be able to continue in the study, and treatment or intervention is usually needed.

A mild, moderate, or severe AE may or may not be serious [see Section 9.2.1]. These terms are used to describe the intensity of a specific event. Medical judgment should be used on a case-by-case basis.

Seriousness, rather than intensity assessment, determines the regulatory reporting obligations.

9.1.3 Relationship to study treatment

Each AE must be assessed by the investigator as to whether or not there is a reasonable possibility of causal relationship to the study treatment, and reported as either related or unrelated. The determination of the likelihood that the study treatment caused the AE will be provided by the investigator.

9.1.4 Reporting of adverse events

The investigator will ask the subject to report all AEs at each study visit, including the telephone calls.

All AEs with an onset date after signing of informed consent and up to EOS for subjects that are not enrolled in ID-078A303 extension study must be recorded on AE pages of the eCRF.

All AEs with an onset date after signing of informed consent, and up to enrollment in the ID-078A303 (i.e., ID-078A301 EOT) for subjects that are participating in the extension study, must be recorded on AE pages of the ID-078A301 eCRF.

9.1.5 Follow-up of adverse events

AEs still ongoing more than 30 days after EOS for subjects that are not enrolled in the ID-078A303 extension study must be followed up until they are no longer considered clinically relevant or until stabilization. The follow-up information obtained after the subject's EOS telephone call will not be collected by Idorsia.

For subjects enrolled in ID-078A303, AEs that are ongoing at ID-078A301 EOT will be followed up in the extension study and reported in the ID-078A303 eCRF on a dedicated page.

9.2 Serious adverse events

9.2.1 Definitions of serious adverse events

An SAE is defined by the ICH guidelines as any AE fulfilling at least one of the following criteria:

- Fatal.

- Life-threatening: Refers to an event in which the subject was at risk of death at the time of the event. It does not refer to an event that hypothetically might have caused death had it been more severe.
- Requiring in-patient hospitalization or prolongation of existing hospitalization.
- Resulting in persistent or significant disability or incapacity.
- Congenital anomaly or birth defect.
- Medically significant: Refers to important medical events that may not immediately result in death, be life-threatening, or require hospitalization but may be considered to be SAEs when, based upon appropriate medical judgment, they may jeopardize the subject, and may require medical or surgical intervention to prevent one of the outcomes listed in the definitions above.

The following reasons for hospitalization are not considered as SAEs:

- Hospitalization for cosmetic elective surgery, or social and/or convenience reasons.
- Hospitalization for pre-planned (i.e., planned prior to signing informed consent) surgery or standard monitoring of a pre-existing disease or medical condition that did not worsen, e.g., hospitalization for coronary angiography in a subject with stable angina pectoris.

However, complications that occur during hospitalization are AEs or SAEs (e.g., if a complication prolongs hospitalization).

9.2.2 Reporting of serious adverse events

All SAEs occurring after signing of informed consent up to EOS must be reported on AE pages in the eCRF and on an SAE form, regardless of the investigator-attributed causal relationship with study treatment or study-mandated procedures.

All SAEs with an onset date after signing of informed consent and up to enrollment in ID-078A303 (i.e., ID-078A301 EOT) for subjects that are participating in the extension study must be recorded on AE pages of the ID-078A301 eCRF.

An SAE is defined as related to protocol-mandated procedures if it appears to have a reasonable possibility of a causal relationship to either the study design or to protocol-mandated procedures (e.g., discontinuation of a subject's previous treatment during a washout period, leading to exacerbation of underlying disease).

9.2.3 Follow-up of serious adverse events

SAEs still ongoing more than 30 days after EOS must be followed up until resolution or stabilization, or until the event outcome is provided. The follow-up information obtained

after the subject's EOS telephone call must be reported to Idorsia Global Drug Safety, but it is not recorded in the eCRF.

For subjects enrolled in ID-078A303, SAEs that are ongoing at ID-078A301 EOT will be followed up in the extension study and reported in the ID-078A303 eCRF on a dedicated page.

9.2.4 After the 30-day follow-up period

New SAEs occurring after the 30-day follow-up period must be reported to Idorsia Global Drug Safety within 24 hours of the investigator's knowledge of the event, **only** if considered by the investigator to be causally related to previous exposure to the study treatment.

9.2.5 Reporting procedures

All SAEs must be reported by the investigator to Idorsia Global Drug Safety within 24 hours of the investigator's first knowledge of the event.

All SAEs must be recorded on an SAE form, irrespective of the study treatment received by the subject, and whether or not this event is considered by the investigator to be related to study treatment.

The SAE forms must be sent to Idorsia Global Drug Safety (contact details are provided on the SAE form). The investigator must complete the SAE form in English, and must assess the event's causal relationship to the study treatment.

Any relevant information from source documents regarding the SAE, e.g., hospital notes or discharge summaries, etc., must be summarized on the SAE form.

Follow-up information about a previously reported SAE must also be reported within 24 hours of receiving it. Idorsia Global Drug Safety personnel may contact the investigator to obtain further information.

If the subject is hospitalized in a hospital other than the study site, it is the investigator's responsibility to contact this hospital to obtain all SAE-relevant information and documentation.

The expectedness of an adverse reaction is determined by Idorsia in the reference safety information (RSI) section provided in the most recent version of the IB for ACT-541468 [ACT-541468 IB]. Any SAE that is assessed as related and unexpected against the RSI of the ACT-541468 IB [ACT-541468 IB] is known as a SUSAR and must be reported by Idorsia to concerned health authorities (including the EudraVigilance database if the study is conducted in Europe), IECs/IRBs and investigators.

